17.3.1. ADDITIONAL ANALYSIS

Proportion of patients achieve hsCRP <2 mg/L at Weeks 12, 24, and 52 for whom baseline hsCRP >2 mg/L will be analysed by Cochran–Mantel–Haenszel (CMH) method adjusted by stratification factor. Summary statistics and treatment difference estimates are based on observed data with no imputation for the missing data.

18. SAFETY OUTCOMES

All outputs for safety outcomes will be based on the Safety Analysis Set.

There will be no statistical comparisons between the treatment groups for safety data, unless otherwise specified with the relevant section.

18.1. ADVERSE EVENTS

Adverse Events (AEs) will be coded using MedDRA, Version 20.1.

Treatment emergent adverse events (TEAEs) are defined as AEs that started or worsened in severity after the first dose of double-blind study medication and prior to the last date of study medication + 30 days. AEs that occurred on day 1 will be only be determined as TEAE if the site indicated it occurred after first dose on the AE CRF.

See [Appendix 2](#) for handling of partial dates for AEs. In the case where it is not possible to define an AE as treatment emergent or not, the AE will be classified by the worst case scenario, i.e. treatment emergent.

An overall summary of number of patients within each of the categories described in the sub-section below, will be provided as specified in the templates. Listings will include TEAEs and Non-TEAEs.

18.1.1. ALL TEAEs

Incidence of TEAEs will be presented by System Organ Class (SOC) and Preferred Term (PT) and also broken down further by maximum severity and relationship to study medication. TEAEs will also be presented by PT in descending frequency. Adverse events by the subgroups in [Section 17.2.4](#) with the exception of baseline LDL subgroup will also be presented.

18.1.2. SEVERITY

Severity is classed as mild/ moderate/ severe (increasing severity). TEAEs starting after the first dose of double-blind study medication with a missing severity will be classified according to worst case scenario, ie, as severe. If a subject reports a TEAE more than once within that SOC/ PT, the AE with the worst case severity will be used in the corresponding severity summaries.

18.1.3. RELATIONSHIP TO STUDY MEDICATION

Relationship, as indicated by the Investigator, is “not related” if the TEAE is “not related” or “unlikely related” A “related” TEAE is defined as a TEAE with a relationship of “possibly related”, “probably related”, or “definitely related” to study medication. TEAEs with a missing relationship to study medication will be regarded as “related” to study medication. If a subject reports the same AE more than once within that SOC/ PT, the AE with the worst case relationship to study medication will be used in the corresponding relationship summaries.

18.1.4. TEAEs LEADING TO DISCONTINUATION OF STUDY MEDICATION

TEAEs leading to permanent discontinuation of study medication will be identified by using the

Statistical Analysis Plan

response of 'Drug Withdrawn/Permanently discontinued' on the Action Taken With Study Drug Field on the AE eCRF page. For TEAEs leading to discontinuation of study medication, summaries of incidence rates (frequencies and percentages) by SOC and PT will be prepared.

18.1.5. SERIOUS ADVERSE EVENTS

Serious adverse events (SAEs) are those events recorded as "Serious" on the Adverse Events page of the (e)CRF. A summary of serious TEAEs by SOC and PT will be prepared. Serious TEAEs will also be presented by PT in descending frequency.

18.1.6. ADVERSE EVENTS OF SPECIAL INTEREST (AESI)

Adverse events of special interest will be identified by pre-specified MedDRA preferred terms provided by Esperion Therapeutics Inc. (see [Appendix 5](#)). These events will be summarized by AESI category, SOC and PT. All AESI will be summarized by severity and relationship to study medication. In addition, AESI will be evaluated by monitoring safety labs as detailed in [section 18.4](#).

18.2. DEATHS

If any patients die during the study, as recorded on the Death Event page of the eCRF , the information will be presented in a data listing. Deaths will be categorized as cardiovascular (CV) death (MACE) or non-CV death (non-MACE).

18.3. CLINICAL ENDPOINTS

Clinical endpoints will be monitored and adjudicated by an independent blinded expert CEC for this study. The following clinical endpoints will be tabulated:

- CV death (MACE)
- Non-CV death (non-MACE)
- Nonfatal myocardial infarction [MI] (MACE)
- Nonfatal stroke (MACE)
- Hospitalization for unstable angina (MACE)
- Coronary revascularization (MACE)
- Non-coronary arterial revascularization (non-MACE)
- Hospitalization for heart failure (non-MACE)

Statistical Analysis Plan

Additional details regarding clinical endpoints and clinical endpoint definitions will be included in CEC charter. The number of patients with at least one adjudicated event and incidences and percentage of patients with each event will be presented in a table.

18.4. SAFETY LABORATORY EVALUATIONS

Results from the central laboratory will be included in the reporting of this study for Hematology, Blood Chemistry, Lipids, Coagulation, HbA1C, hsCRP and Urinalysis. A list of laboratory assessments to be included in the outputs is included in Protocol, Section 11.1.6.1.

Presentations will use SI Units and conventional units.

Quantitative laboratory measurements reported as “< X”, i.e. below the lower limit of quantification (BLQ), or “> X”, i.e. above the upper limit of quantification (ULQ), will be converted to X for the purpose of quantitative summaries, but will be presented as recorded, i.e. as “< X” or “> X” in the listings.

The formula to calculate eGFR is: $eGFR = 186 \times (\text{Creatinine} / 88.4)^{-1.154} \times (\text{Age})^{-0.203} \times (0.742 \text{ if female}) \times (1.210 \text{ if black})$, where creatinine is in mmol/L.

Summaries for all lab results, including unscheduled visit values, will be included for below analyses:
 Observed and change/percent change from baseline by visit (for quantitative measurements).

Shift from baseline by visit according to normal ranges.

Shift from baseline according to normal ranges for HbA1c and glucose by history of diabetes and visit.
 eGFR and values of CK will be summarized by treatment group and by baseline eGFR categories (low, normal, high).

Potential Hy’s law cases (>3 × ULN for either ALT or AST AND Total Bilirubin >2 × ULN in the setting of no known other cause) will be tabulated and listed.

Laboratory abnormalities in parameters of interest

- ALT or AST (> 3x ULN , >5xULN)
- TB (>2x ULN)
- CK (> 5x ULN) and (>10x ULN)
- Fasting Blood Glucose (≤50 mg/dL, ≥126 mg/dL) by history of diabetes
- HbA1c (≥6.5%) by history of diabetes
- Creatinine (change from baseline for >1 mg/dL)
- eGFR (< 15 mL/min/1.73m², 15 –< 30 mL/min/1.73m²)
- Hgb (decrease from baseline for ≥2 g/dL)
- Hgb (<8 g/dL)

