10.2.4. Treatment Week 0 (Visit T1; Day 1)

Prior to scheduling Visit T1, review the information collected at Visits S1, S2, and S3 to evaluate whether the patient continues to meet eligibility criteria.

- If the patient meets eligibility criteria, then schedule the Visit T1 and proceed with the Visit T1 procedures

If the patient has met all inclusion criteria and none of the exclusion criteria, the patient may be randomized into the double-blind treatment period. Patients who fail to meet any entry criterion prior to randomization are considered to be screen failures, will not be randomized into a treatment group, and are not required to return for additional visits. Patients are considered randomized once all eligibility criteria are confirmed and a randomization number is obtained by the IWRS on the day of first dose.

The patient will undergo the following assessments and procedures at (Visit T1)

- Concomitant and prohibited medication review (ongoing)
- Assess AEs, SAEs, and potential clinical endpoints
- Physical examination (PE)
- Weight
- 12-Lead electrocardiogram (ECG)

- Vital signs
- Clinical laboratory evaluations:
 - Hematology, blood chemistry, and urinalysis
Note: Urine pregnancy test (for females of childbearing potential)
 - Coagulation in patients on vitamin K antagonists only (and repeat 3-5 days later)
 - Basic fasting lipids (TC, calculated LDL-C, HDL-C, non-HDL-C, and TG)
 - apoB
 - HbA_{1C}
 - hs-CRP
- Review inclusion/exclusion criteria to establish patient eligibility
- Conduct diet and exercise counseling
- IWRS contact to obtain the patient randomization number and MED ID number for double-blind study drug
- Dispense IMP and provide dosing instructions (one 100-day supply bottle)
- Return of placebo tablets, record compliance and ensure patient meets eligibility criteria
- Schedule next visit

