10.2.5. Treatment Week 4 (Visit T2; 29 ±3 days)

If the patient is withdrawing early from the study at this visit, proceed to [Section 10.3.2](#) for the list of the required assessments.

If the patient is withdrawing from IMP treatment at this visit, proceed to [Section 10.3.2](#) for the list of the required assessments. The patient will be asked to continue to be followed for safety using the protocol-specified visit schedule.

Patients refusing to continue to return to the clinic for protocol assessments after withdrawing from IMP treatment will be asked to participate in phone calls from the site at protocol-specified visits, or at a minimum at 52 weeks, to inquire about the patient's current health status and collect information on AEs (eg, recent procedures, hospitalizations, and if the patient has died, the cause of death). If the patient consents for telephone contacts, schedule the next protocol-specified visit.

Patients will undergo the following assessments and procedures at Week 4 (Visit T2):

- Concomitant and prohibited medication review (ongoing)
- Assess AEs, SAEs, and potential clinical endpoints since last visit (ongoing)
- Weight
- Vital signs

- Clinical laboratory evaluations:
 - Hematology, blood chemistry, and urinalysis
 - Basic fasting lipids (TC, calculated LDL-C, HDL-C, non-HDL-C, and TG)
- Conduct diet and exercise counseling
- Return of IMP; assessment and recording of IMP compliance
- Re-dispense IMP container from Visit T1 to patient for continued dosing and provide dosing instruction
- Schedule next visit

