11.1.6. Clinical Laboratory Tests

11.1.6.1. Laboratory Parameters (Safety)

Patients will be in a seated position during the blood collection. Clinical laboratory parameters and tests will include those listed in [Table 5](#). Collection schedule, schedule of laboratory parameters by visit, and instructions are in the Clinical Laboratory Manual provided by Central Laboratory.

Table 5: Clinical Laboratory Parameters (Safety)

Clinical Laboratory Test	Clinical Laboratory Test
Hematology 
 • Hematocrit (Hct) • Hemoglobin (Hgb) • Mean corpuscular hemoglobin (MCH) • Mean corpuscular hemoglobin concentration (MCHC) • Mean corpuscular volume (MCV) • Platelet count • Red blood (RBC) cell count • White blood (WBC) cell count with differential (absolute and %) 	Blood Chemistry (serum, fasting) 
 • Albumin (Alb) • Alkaline phosphatase (ALK-P) • Alanine aminotransferase (ALT; SGPT) • Aspartate aminotransferase (AST; SGOT) • Blood urea nitrogen (BUN) • Calcium (Ca) • Carbon dioxide (CO₂) • Chloride (Cl) • Creatinine • Creatine kinase (CK) • Glucose • Lactate dehydrogenase (LDH) • Phosphorus • Potassium (K) • Sodium (Na) • Total and direct bilirubin (TB)^a • Total protein • Uric acid
Urinalysis (Dipstick) 
 • Clarity • Bilirubin • Color • Glucose • Ketones • Leukocyte esterase • Nitrite • Occult blood • pH • Protein • Specific gravity • Urobilinogen 	

Table 5: Clinical Laboratory Parameters (Safety) (Continued)

Clinical Laboratory Test	Clinical Laboratory Test

Urinalysis (Microscopic)-only if urine dipstick abnormal
 
 • Bacteria • Casts • Crystals • Epithelial cells • Red blood cell (RBC) • WBC 	
Coagulation (screening for all patients, T1 and 3-5 days after T1 in patients receiving anticoagulation therapy, only)
 
 • Prothrombin time (PT) • International normalized ratio (INR)

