11.1.6.3.1. Monitoring and Management of Elevated Liver Function Tests

If at any time after randomization a patient experiences a new ALT and/or AST $>3 \times$ ULN, the patient will undergo repeat confirmatory liver function test (LFT) assessment as soon as is reasonably possible, preferably within 3 to 7 days of the laboratory result becoming available.

Repeat LFT assessment will include: 1) measurement of ALT, AST, alkaline phosphatase, total and direct bilirubin, prothrombin time (PT)/international normalized ratio (INR), eosinophil count, CK, antihepatitis A virus (total), HBsAg (confirmation of screening measurement), HCV (confirmation of screening measurement), and anti-cytomegalovirus/immunoglobulin M; 2) history of concomitant medication use; 3) history of exposure to environmental chemical agents, including ethanol; and 4) query for related symptoms. Additionally, further testing such as liver ultrasound or magnetic resonance imaging (MRI) scanning may be warranted to rule out additional pathology depending on clinical presentation and should be discussed with the Sponsor personnel or the authorized Medical Monitor.

- If repeat LFT assessment confirms ALT and/or AST $>3 \times$ ULN, consideration should be given to withdrawing the patient and administering no further doses of study drug. At the investigator's discretion, study drug may be interrupted and the patient rechallenged with study drug after LFTs have returned to baseline levels.
- If repeat LFT assessment confirms ALT and/or AST $>5 \times$ ULN, patient should be withdrawn from IMP treatment, but will be asked to continue to be followed for safety using the protocol-specified visit schedule (see [Appendix 1](#)) or more frequently if deemed by the investigator.
- If repeat LFT assessment confirms ALT and/or AST $>3 \times$ ULN in addition to any of the following, the patient should be given no further IMP treatment, but will be asked

to continue to be followed for safety using the protocol-specified visit schedule (see [Appendix 1](#)) or more frequently if deemed by the investigator:

- TB $>2 \times$ ULN

Note: In the case of patients with Gilbert's disease, TB will be fractionated and the determination of $2 \times$ ULN will be based upon direct (conjugated) bilirubin.

- INR $>1.5 \times$ ULN (unless the patient is on stable dose of anticoagulation medication)

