- ² An optional visit between Visits S1 and S2 may be completed if the patient's DBP and/or SBP meet the exclusion criteria levels. Patients may randomize after blood pressure medications have been adjusted, the patients have been on stable doses of blood pressure medications for at least 2 weeks, and the repeat blood pressure values (DBP and/or SBP) do not meet exclusionary values. An optional visit between Visit S1 and S2 may be completed to determine eligibility if the patient's eGFR, ALT, AST, and/or TB meet exclusion criteria levels. If this optional visit is completed, the repeated value will be used to determine eligibility.
- ³ All procedures will be completed for all patients at either End of Study (EOS) if completing the study or early withdrawal.
- ⁴ Body weight will be measured while fasting, using consistent scales, after voiding, and without shoes and outerwear (eg, coats).
- ⁵ Single 12-lead ECG will be collected prior to any blood sample collection.
- ⁶ Vital signs will include DBP, SBP, and HR and will be collected prior to any blood sample collection. Patient will rest for 5 minutes prior to assessments
- ⁷ Serology for HBsAg, HCV
- ⁸ Serum pregnancy test completed in premenopausal women only. FSH test is completed in women <55 years old and >1 year without menses. Urine pregnancy test in women of childbearing potential just prior to randomization.
- ⁹ Clinical safety labs include hematology, blood chemistry, and urinalysis at all visits. Coagulation is included at Screening (Visit S1) for all patients, Baseline (Visit T1) and 3-5 days after Visit T1 only if on anticoagulants). Please refer to laboratory manual for detailed schedule of tests. A local laboratory may be used for assessment at 3-5 days after Visit T1.
- ¹⁰ Basic fasting (minimum of 10 hours) lipids include total cholesterol, calculated LDL-C, HDL-C, non-HDL-C, and triglycerides.
- ¹¹ Diet and exercise counseling per local and/or regional guidelines for the management of hyperlipidemia.
- ¹² IWRS contact at either an early withdrawal or an EOS visit to register study discontinuation visit date.
- ¹³ Depending upon the length of time between visits, 1 or 2 bottles of study medication will be dispensed as instructed by IWRS.
- ¹⁴ If patient is discontinuing treatment and completing the EOS visit, but will be continuing in the study either by returning to clinic or by phone, continue to schedule study visits for the patient according to the protocol Schedule of Events

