6.4. VISIT WINDOWING

Protocol-defined assessments will be “slotted” to study weeks based on collection date and applying the rules summarized in the following table. If there is more than one scheduled visit in a visit window, the visit closest to the target date will be used. If there is a tie between the numbers of days from the target date, the visit after the target date will be used. Unscheduled visits that fall within the protocol-defined visit windows will be summarized in the by-visit analyses if there is no scheduled visit available. If there is more than one unscheduled visit within the protocol-defined visit window and no scheduled visit available, the unscheduled visit closest to the scheduled visit date will be used. If there is a tie between the numbers of days from the target date, the visit after the target date will be used.

However, exposure data obtained from the drug accountability and administration CRF will be summarized and listed according to nominal visit information.

Analysis Visit	S1	S2	S3	T1	T2	T3	T4	T5	T6	T7
Study Week	-5	-4	-1	week 0	4	8	12	24	36	52/EOS
Target Study Day	-35	-28	-7	1	29	57	85	168	252	365
Analysis Visit Windows	$[-\infty, -32]$	$[-31, -18]$	$[-17, -1]$	$[1, 1]$	$[2, 43]$	$[44, 71]$	$[72, 127]$	$[128, 211]$	$[212, 309]$	$[310, \infty]$

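### The only scheduled post-dose PT/INR is labelled Week 4 if measured centrally and has no place in the SAP summaries if measured locally

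*SAP*

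**What the plan says.** **When coagulation is drawn.** Protocol 11.1.6.1 (Table 5) schedules PT/INR at screening for everyone, then "T1 and 3-5 days after T1 in patients receiving anticoagulation therapy, only". Footnote 9 of the schedule of events (Protocol Appendix 1) agrees: "Baseline (Visit T1) and 3-5 days after Visit T1 only if on anticoagulants". Protocol 10.2.4 describes a narrower group: "Coagulation in patients on vitamin K antagonists only (and repeat 3-5 days later". From Week 4 onward the visit lists contain "Hematology, blood chemistry, and urinalysis" and no coagulation (Protocol 10.2.5, 10.2.7, 10.2.8, 10.2.10). One further post-dose INR is possible but conditional. The repeat panel after a new ALT or AST above 3 × ULN includes "prothrombin time (PT)/international normalized ratio (INR), eosinophil count" (Protocol 11.1.6.3.1).

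**Who may run it.** Footnote 9 adds: "A local laboratory may be used for assessment at 3-5 days after Visit T1".

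**What is reported.** SAP 18.4 states: "Results from the central laboratory will be included in the reporting of this study for Hematology, Blood Chemistry, Lipids, Coagulation". It plans observed values, change from baseline and shifts by visit, and says nothing on local results.

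**How a result gets its time label.** SAP 6.4 slots assessments "to study weeks based on collection date and applying the rules summarized in the following table". In that table T1 is Day 1 alone and Week 4 is Days 2 to 43 with target Day 29. There is no analysis visit between them.

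**The concern.** The protocol asks a defined group of patients for an extra blood draw a few days after study drug starts, paired with a draw at T1. One would expect the SAP to show the change between the two by treatment group, at the right time, in everyone tested. Its reporting rules were written around the main clinic visits and do not fit this draw. The time label is wrong for central results, and local results have no stated handling.

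What is at stake is the accuracy and completeness of the only planned post-dose coagulation data. A table reader would see a Week 4 coagulation result although none was scheduled then. Whether a patient contributes would depend on a site's choice of laboratory. No efficacy endpoint, error rate or sample-size figure is involved.

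**Working it through.** The plan states no figure on this point, so there is none to reproduce. The check applies the SAP's own rules to the draw.

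**1. Study day.** SAP 6.1 gives Study Day = (date − reference date) + 1 on or after first dose. With first dose at T1:
- 3 days later: 3 + 1 = Day 4
- 4 days later: 4 + 1 = Day 5
- 5 days later: 5 + 1 = Day 6

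**2. Window.** All three days lie in [2, 43], so the label is Week 4. Distance to target: 29 − 4 = 25, 29 − 5 = 24, 29 − 6 = 23 days. The protocol's own Week 4 visit is Day 29 ± 3, that is Days 26-32. The latest draw (Day 6) is 26 − 6 = 20 days before that visit opens.

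**3. Competing values.** No coagulation is scheduled at Week 4, so normally nothing competes. The exception is the INR in the repeat liver panel. Where several unscheduled values share a window and no scheduled one is available, SAP 6.4 keeps the one closest to target. It applies the same criterion among scheduled visits. For a second INR on Days 7-43, the largest distance from Day 29 is max(29 − 7, 43 − 29) = max(22, 14) = 22 days. The Day 4-6 draw is at least 23 days away, so the second value wins wherever in Days 7-43 it falls. A liver-test alert from the Week 4 visit, repeated 3-7 days after the result, would start from 26 + 3 = Day 29 and reach 32 + 7 = Day 39, plus laboratory turnaround (not stated). Displacement assumes that both draws have the same status. The SAP does not say whether the Day 4-6 draw counts as scheduled. If it does and the liver-panel INR does not, the Day 4-6 value keeps the slot.

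**4. Source.** The two documents side by side:

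| | Protocol, 3-5 day draw | SAP 18.4 |
|---|---|---|
| Central result | allowed | reported, under Week 4 |
| Local result | allowed for this draw | no rule |

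**5. Comparability of rows.** Under SAP 6.2 the coagulation baseline is the last non-missing value on or before first dose. That is the screening value for patients not tested at T1, and the T1 value for those who were. The observed baseline row therefore covers nearly all randomized patients, while the row labelled Week 4 holds almost only the tested subgroup. The two observed means are not comparable. Within-patient change is unaffected. SAP 18.4 plans no coagulation summary by anticoagulant use.

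**The case against.** The best defence is that central data are mislabelled, not lost. Because no coagulation is scheduled at Week 4, the row carrying that label would consist almost entirely of Day 4-6 draws. Change from baseline is paired and valid, SAP 6.1 calls for study day to be shown, and SAP 6.3 puts scheduled and unscheduled data in the listings. All of this stands. A reader might infer that the early INR cannot be interpreted at all, and the documents do not support that for central values.

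Nor does the SAP say that local results are excluded. It says that central ones will be included. SAP Appendix 1 wants every CRF variable with data listed, and Protocol 11.2.7.3 recognizes local reference ranges. So calling local values dropped also goes too far. If entered on the eCRF they should appear in listings; whether they are entered is not stated. What remains is that they have no stated route into the summary tables, and a listing is not a by-arm summary.

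It is also tempting to call this draw a drug-interaction check that the SAP defeats. A draw before and shortly after starting study drug, limited to anticoagulated patients, invites that reading, but neither document gives its purpose. It may serve individual patient monitoring, which works whatever label the SAP applies. Coagulation is not among the adverse events of special interest in Protocol 11.4 or the laboratory parameters of interest in SAP 18.4, and safety output is descriptive. This limits the weight of the point but does not remove the mislabelling or the gap for local values.

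**Conclusion.** The point holds in a limited form. Under the SAP as written, the only scheduled post-dose PT/INR is shown under Week 4 although taken 23-25 days before that target. It can be displaced by an INR from a repeat liver panel, and it has no place in the by-visit and shift summaries if a local laboratory ran it. The post-dose coagulation summary is mislabelled in time and possibly incomplete. Efficacy conclusions are untouched.

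The number of patients affected cannot be derived: the documents give neither the share on anticoagulants nor the share of draws sent to local laboratories. For scale only, an assumed 3% to 10% on anticoagulants would be 0.03 × 750 = 22.5 to 0.10 × 750 = 75 patients. The denominator is itself unsettled, because Protocol 10.2.4 limits the draw to vitamin K antagonist users while Table 5 and Appendix 1 footnote 9 refer to anticoagulation more broadly.

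The conclusion assumes that first dose is at T1, that the window rules are applied per laboratory parameter, and that the central-laboratory sentence in SAP 18.4 defines the source for the summary tables.

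**What to change.** - **SAP 6.4:** add a coagulation-only analysis visit for the 3-5 day draw, separate from Week 4. Any window that contains Days 4-6 and closes before Day 26 keeps it clear of the protocol's Week 4 visit. State that liver-panel INRs do not replace this value.
- **SAP 18.4:** include local PT/INR for this time point, flagged by source. Summarize INR change from T1 to this visit by treatment group in the patients tested, and list all values with study day and laboratory.
- **Protocol:** reconcile 10.2.4 with Table 5 and Appendix 1 footnote 9 on who is tested, since this sets the denominator of the new table.

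The cost is a few sentences, one small table and one listing. Local INR values may need eCRF entry if they are not already captured. The drawback is that local and central assays are mixed; the source flag makes this visible and allows a central-only view. The SAP addendum of December 2018 reports that the planned analyses were complete and unblinded, so output added after that point should be labelled post hoc.
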